8.0 STATISTICAL ANALYSES

8.1 Subject Disposition

Frequency counts and percentages will be tabulated for all subjects who complete or early discontinue from the study drug. Reasons for early discontinuation from study drug will be summarized by the highest titrated dose level.

8.2 Protocol Deviations

Subjects with major protocol deviations and violations will be listed and summarized by the highest dose level which a subject was titrated to and for each study site and for overall subjects. Major protocol deviations or violations may include but not limited to the followings:

Subjects who entered the study even though they did not satisfy the entry criteria;

1. Subjects who developed withdrawal criteria during the study but were not withdrawn from study medication;
2. Subjects who received prohibited medication.

Subjects with one or more protocol deviations or violations in the same category/type will be counted once for that category.

Protocol deviations and violations will be captured by searching relevant data fields reported in the clinical database using computer algorithms and site monitoring by clinical research associates. All deviations and violations will be reviewed by medical monitors. Final determination of major deviations and violations will be reviewed by the study team at regular intervals throughout the trial (including the clinical study manager, the Medical Monitor, and the statistician).

Subjects who have protocol deviation/violation will also be presented in a data listing.

8.3 Demographic and Baseline Disease Characteristics

Demographic and baseline characteristics including age (years) sex, race, ethnicity, smoking history, height (cm), weight (kg), body mass index (BMI; kg/m²), and time since diagnosis of chronic noncancer pain will be summarized descriptively by highest titration dose level.

General medical history including past or present clinically significant medical conditions collected at screening will be summarized and presented in a data listing. Medical history of noncancer pain onset will be summarized.

Age will be calculated as follows:

$$\text{Age} = \frac{\text{Date of informed consent} - \text{Date of birth}}{365.25} \text{ rounded down to the integer value in years.}$$

BMI will be calculated as follows:

$$\text{BMI} = (\text{weight in kilograms}) / (\text{height in meters})^2$$

Time to noncancer pain onset will be calculated as follows:

$$\frac{\text{Date of informed consent} - \text{Date of onset noncancer pain}}{365.25} \text{ rounded off to one decimal place in year.}$$

Partial dates for date of onset in the calculation will be imputed. If year and month in the initial diagnosis are presented and day is missing, the first day of the month will be imputed. If year is presented but month/day is missing, missing day and month will be imputed as January 1. No imputation will be done if the year is missing.

8.4 Prior and Concomitant Medication

Prior and concomitant medications are recorded on the electronic case report form (eCRF) and coded to anatomical, therapeutic, or chemical code and preferred drug name using the World Health Organization (WHO) Dictionary (Version WHODRUG2014MAR01 WHO Drug Dictionary Enhanced [DDE]).

Prior medications are defined as medications taken before or on the date of first dose of NKTR-181 in 14-181-08 (Visit 3), including medications continued during treatment.

Concomitant medications are defined as medications taken on or after the date of first dose of NKTR-181 in 14-181-08 (Visit 3) including medications initiated prior to the date of first dose and continued during treatment, and medications initiated on or after the date of first dose.

Prior and concomitant medications will be tabulated separately for the Safety Population by WHO DDE ATC level 2 classifications, preferred term. The number and percent of subjects taking medication will be calculated. If the ATC level 2 classification is missing, the next non-missing level of classification will be used (level 1). If a subject reports the same ATC level 2 classification multiple times, the ATC level 2 classification will be incremented by one. As with ATC level 2 classification, if a subject reported multiple medications within the same preferred

term, the preferred term increments by one. Percentages will be calculated using the total number of subjects in the corresponding dose level in the Safety Population.

Prior and concomitant medications will be presented in a data listing.

8.5 Study Drug Exposure and Drug Compliance

Duration of exposure to study drug, cumulative dose of the study drug, and compliance of the study drug will be summarized for NKTR-181 on the Safety Analysis Set for the overall study period based on the Safety Analysis Set. The exposure duration of the study drug will be also summarized by time interval (e.g., ≥ 1 month, ≥ 2 months, ..., ≥ 12 months, and > 13 months).

The exposure duration (days) will be calculated as the number of days exposed to study drug: date of last dose - the date of first dose + 1.

The cumulative dose (mg) will be calculated as the sum of the number of tablets taken times the dosage per tablets at each dosage level. A subject's compliance of the study drug will be calculated according to the following:

$$\text{Compliance} = \frac{\text{number of tablets taken}}{\text{number of tablets planned}} \times 100$$

Compliance will be calculated based on the drug administration recorded in the CRFs. The number of tablets taken will be calculated as the total number of tablets dispensed minus the total number of tablets returned. If the number of returned tablets is missing due to any reason, it will be assumed that the subject took all dispensed tablets during that period. For those subjects who are lost to follow-up, it will be assumed that they took the number of dispensed tablets up until the last day of contact.

The number of tablets planned will be calculated as the prescribed number of tablets per day multiplied by the number of days potentially exposed to the study drug:

$$n \times (\text{the date of last dose} - \text{the date of first dose} + 1)$$

where n is related to the dose level. n is 2 for 100mg and 200mg, n is 4 for 300mg and 400mg, and n is 6 for 500mg and 600mg. The number of tablets planned will be adjusted for the first dose and the last dose time of the study drug.

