6.2 Treatment Period (Visits 3-20)

At Visit 3, subjects will be evaluated for entry into the Treatment Period. The Investigator or qualified sub-Investigator will complete the COWS ([Wesson, 2003](#)). The subject must score ≤ 12 to continue in the Treatment Period. Subjects who score greater than 12 will complete their Screening Period and end study participation and will be treated appropriately for withdrawal according to the investigators clinical practice. A Rollover Subject's last COWS assessment during Study 14-181-07 or Study 14-181-12 will satisfy this requirement. De Novo Subjects will discontinue all current analgesics including their prior opioid medication.

All subjects will begin dosing with 100-mg NKTR-181 BID with dose escalation in stepwise increments of 100-mg (e.g., from 200-mg BID to 300-mg BID) up to a maximum dose of 600-mg BID. All dose escalations will occur prior to visit 10. The dose of NKTR-181 will not exceed 600 mg BID in this study. Subjects will be instructed to take study drug BID, preferably at 8 AM and 8 PM. Subjects will also receive training on the recognition and management of constipation and other opioid related side effects. Side effects should be managed according to standard of care practices.

If a subject cannot tolerate 100-mg NKTR-181 BID, the subject will be discontinued from the study; these subjects will be required to complete the Early Termination (ET) visit (Visit 21/ET) and safety follow-up requirements. Refer to the Schedule of Assessments (Section 1.2) for complete information regarding all assessments to be completed at the ET Visit and safety follow-up requirements.

Within 4-10 days after receiving the first dose of NKTR-181, subjects will return to the clinic at which time the Investigator will assess for tolerability and effectiveness. **Tolerability** and **effectiveness** will be assessed based on Investigator (or qualified sub-Investigator) clinical judgment. The Investigator (or qualified sub-Investigator) will determine whether the subject should remain at the current dose or titrate to the next dose level.

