Following 51 weeks of NKTR-181 treatment, subjects will begin a 1-week taper from study drug. The NKTR-181 dose will be decreased over the 1-week period until all subjects are receiving 100-mg BID for at least 2 days. Subjects will return to the site for their End of Treatment visit (Visit 22/EOT). Following completion of Visit 22/EOT **or** completion of an ET Visit at any time after receiving study drug, subjects will proceed to the Safety Follow-Up Period.

The COWS and SOWS will be administered according to the Schedule of Assessments (Section 1.2) to monitor for opioid withdrawal. Subjects experiencing opioid withdrawal will be treated appropriately according to the Investigator's clinical practice.

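### SAP 8.5 multiplies one tablets-per-day value by the whole treatment span, so the compliance summary is misstated for subjects who reach 300 mg BID or more

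*SAP*

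**What the plan says.** SAP 8.5 defines compliance as tablets taken over tablets planned, times 100. For the numerator, "The number of tablets taken will be calculated as the total number of tablets dispensed minus the total number of tablets returned". The denominator is "the prescribed number of tablets per day multiplied by the number of days potentially exposed to the study drug", printed as n times a span, "date of last dose - the date of first dose + 1", which is the same expression the section uses for exposure duration. The daily count is introduced as "where n is related to the dose level" and then given values: "n is 2 for 100mg and 200mg, n is 4 for 300mg and 400mg, and n is 6 for 500mg and 600mg". One adjustment is stated: "The number of tablets planned will be adjusted for the first dose and the last dose time of the study drug".

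Protocol 6.2 makes the daily tablet count vary within a subject. At the start, "All subjects will begin dosing with 100-mg NKTR-181 BID with dose escalation in stepwise increments of 100-mg", to a maximum of 600 mg BID. Rollover Subjects also enter at 100 mg BID (Protocol 6.1.1). Titration visits are 4 to 10 days apart, and the dose may later go up or down. At the end, "The NKTR-181 dose will be decreased over the 1-week period until all subjects are receiving 100-mg BID for at least 2 days".

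**The concern.** A formula with one n and one span describes a fixed-dose study. Here, anyone who reaches 300 mg BID or more has been prescribed at least two different daily tablet counts. Whichever n is chosen, the denominator differs from what was prescribed, and a perfectly adherent subject does not score 100%.

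The SAP also leaves the choice of n open. Sections 8.1 and 8.3 group subjects by highest titrated dose, section 7.2 defines a stable dose at Visit 10, and a completer's last dose is the taper dose. Two programmers could work from the same text and report very different figures.

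At stake is whether the summary can be interpreted for the Safety Analysis Set. With n from the highest dose, the error is largest in subjects who stop soon after titration. It can also hide over-use: in the Day 42 example below, a subject who took 252 tablets against 168 prescribed (150%) would score 252/252 = 100%.

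**Working it through.** **Inputs from the documents.** Tablets per dose for 100, 200, 300, 400, 500 and 600 mg are 1, 1, 2, 2, 3 and 3 (Protocol synopsis and 7.1.1). Dosing is twice daily. Titration visits are 4 to 10 days apart. Completers have 51 weeks of treatment and then a 1-week taper: 357 + 7 = 364 days (Protocol 6.2).

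**Assumptions.** Full adherence; equal steps of s days going straight to the top dose, which is then held; no taper for early stoppers. Completers have one of two taper shapes: all 7 days at 100 mg BID (7 × 2 = 14 tablets), or a gradual taper with one day at each intermediate level and the last 2 days at 100 mg BID (22 tablets from 300/400 mg, 26 from 500/600 mg).

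**Reproducing n.** Two doses per day times tablets per dose gives 2, 2, 4, 4, 6, 6. This matches the SAP exactly.

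**Score of a fully adherent subject.** 100 × (sum over dose periods of n_i × days_i) / (n × total days).

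**(a) n from the highest dose, stopping after 7 days at that dose, 7-day steps**

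| Stop | Prescribed and taken | n × days | Score |
|---|---|---|---|
| Day 21, 300 mg | 14 + 14 + 28 = 56 | 4 × 21 = 84 | 66.7% |
| Day 28, 400 mg | 56 + 28 = 84 | 4 × 28 = 112 | 75.0% |
| Day 35, 500 mg | 84 + 42 = 126 | 6 × 35 = 210 | 60.0% |
| Day 42, 600 mg | 126 + 42 = 168 | 6 × 42 = 252 | 66.7% |

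With equal steps the step length cancels (for 300 mg, (2 + 2 + 4)/(3 × 4) = 66.7%), so 4-day or 10-day steps give the same percentages on other stopping days. The shortfall shrinks with longer treatment. At 600 mg with 7-day steps, the score is 276/360 = 76.7% at Day 60, 456/540 = 84.4% at Day 90 and 1008/1092 = 92.3% at Day 182.

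**(b) n from the highest or stable dose, 364-day completer**

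Tablets over the first 357 days:
- 300/400 mg: 2 × 2s + 4 × (357 − 2s) = 1412, 1400, 1388 for s = 4, 7, 10.
- 500/600 mg: 2 × 2s + 4 × 2s + 6 × (357 − 4s) = 2094, 2058, 2022.

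Adding the taper and dividing by 4 × 364 = 1456 or 6 × 364 = 2184:

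| s | 300/400 mg | 500/600 mg |
|---|---|---|
| 4 | 1426 to 1434: 97.9-98.5% | 2108 to 2120: 96.5-97.1% |
| 7 | 1414 to 1422: 97.1-97.7% | 2072 to 2084: 94.9-95.4% |
| 10 | 1402 to 1410: 96.3-96.8% | 2036 to 2048: 93.2-93.8% |

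Five 10-day steps to 600 mg (50 days) would slightly exceed the titration window of at most 10 + 35 = 45 days. The count does not change between 500 and 600 mg, however, so the 10-day row needs only four such steps (40 days).

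**(c) n from the last dose (100 mg BID, n = 2), same completers.** The denominator is 2 × 364 = 728. For 300/400 mg, 1402/728 to 1434/728 = 192.6% to 197.0%. For 500/600 mg, 2036/728 to 2120/728 = 279.7% to 291.2%.

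**(d) Denominator summed by dose period.** Numerator and denominator coincide, for example 2084/2084, so the score is 100.0% in every case.

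**(e) Never above 200 mg BID.** n = 2 on every day: 728/728 = 100% under all of these rules.

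**The case against.** The best defence is that the words allow the correct calculation. The prescribed daily number on a 100 mg BID day is 2, and n is tied to dose level, so a careful programmer could apply n period by period and get 100%. The section already tracks tablets by dosage level for cumulative dose. That reading is available, but it is not what the printed expression says: one n multiplies the whole first-to-last-dose span. Summation by level is written for cumulative dose and not for planned tablets. The adjustment for first and last dose times affects only the ends of the span, not dose changes within it.

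A reader might also infer more than the documents support:
- **That adherent subjects would be classed as non-compliant.** SAP 8.5 sets no threshold and no such category; the ratio is only summarized.
- **That low scores would be taken as intolerance or misuse.** Discontinuation reasons are tabulated directly (SAP 8.1). Misuse goes through MADDERS, with its own accountability form, investigator classification and adjudication (SAP 8.7.4). Neither uses this ratio.
- **That the bias is always downward, or affects everyone.** The direction depends on the unstated dose level, and subjects who stay at 100 or 200 mg BID are untouched.
- **That the tablet counts are wrong.** They reproduce exactly.

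**Conclusion.** The point holds as a defect in a descriptive summary. As printed, the denominator cannot be right for a subject whose daily tablet count changes, and the SAP does not say which dose sets n.

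With n at the highest or stable dose, fully adherent completers at 300 mg BID or more lose about 1.5 to 7 percentage points. Large shortfalls (scores of 60-75%) are confined to those who stop about one step after reaching their top dose. With n at the taper dose, completers score roughly two to three times the true value.

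These sizes rest on full adherence, equal 4 to 10 day steps, direct escalation and the two taper shapes shown. Held doses or later dose changes, which the protocol allows, could move scores outside the ranges. No endpoint, analysis set or sample size depends on the ratio, so the matter is minor.

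**What to change.** In SAP 8.5, define tablets planned as the sum, over each subject's prescribed dose periods, of n for that dose times the days at that dose. State that the periods include titration, later adjustments (also those at unscheduled visits) and the taper. Keep the listed n values and the adjustment for first and last dose times.

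The cost is one formula and its programming. No new data should be needed: cumulative dose in the same section requires tablets by dosage level, and time to dose increase (SAP 8.6.2) requires dose-change dates.

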8.6 Efficacy Endpoint

The mBPI-SF will be assessed at each visit during the study. The mean of the 4 intensity items (3-6) will be calculated and used as a measure of pain severity. The mean of the 7 interference items (9A-9G) will be calculated and used as a measure of Pain interference. Change from baseline to each month (visit) will be calculated for the Pain severity, Pain interference, and each individual score, if applicable.

If there are missing items when the pain severity score and pain interference score are calculated, the mean of the completed items in one dimension (dimensions include pain severity and pain interference) will be imputed to substitute the missing item, provided that more than 50% of the items in one dimension are completed ([Halling, 1999](#)).

The change from baseline and value for mBPI-SF dimensions and individual scores at each visit will be summarized descriptively over time.

In addition, an exploratory analysis will be performed on mBPI. The change from baseline to the end of the long term safety study will be analyzed. Baseline will be considered as last non-missing assessment on or prior to the first dose in this long term safety study (visit 3). The change from baseline will be analyzed using Mixed Model Repeated Measure (MMRM) analysis. The model will include change from baseline as dependent variable, baseline score as a covariate, subject's status (De Novo or Rollover with NKTR-181 or Rollover with Placebo), time, subject's status and time interaction as fixed effects. Point estimates on the Least Squared means over time will be calculated with corresponding 95% confidence intervals different dose levels. These analysis will be applied to both pain intensity and interference based on mBPI. The pain intensity means and LSmeans over time will be present graphically.

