1.1 Study Schematic

1.2 Schedule of Assessments

Assessment Period	Screening Up to 21 days		Treatment* 52 weeks							Follow-Up 14 days		Unscheduled Visit
	1	2 ¹	3	4, 5, 6, 7, 8, 9 (Flexible)	10, 13, 17, & 20	11 & 12	14-16 & 18-19	21/ET ²	22/EOT	23	24/EOS	
Dayse	≤ 21 days prior to Visit 3		1	Every 4-10 Days after previous visit	Every 30 (- 3)	Every 30 (- 3)	Every 30 (- 3)	D357 (+ 3)	D364 (+ 3)	72 hours	14 (± 2)	
Written informed consent	X											
Inclusion/exclusion criteria	X	X	X									
Demographics ³	X											
PHQ-8 ⁴	X											
Medical history ⁵	X											
Alcohol breath test ⁶	X											
Physical examination ⁷	X											
Vital signs ⁸	X		X	X	X				X	X		X
12-lead electrocardiogram ⁹	X				X				X			X
Clinical laboratory tests ¹⁰	X		X	X	X	X		X	X	X	X	X
Pregnancy test ¹¹	X		X		X				X			X
Urine drug screen ¹²	X		X	X	X							
eC-SSRS ¹³	X		X		X			X	X			
Taper opioid analgesics ¹⁴		X										
Dose titration assessment				X								
mBPI-SF ¹⁵			X	X	X	X	X		X			X
COWS		X ¹⁶	X ¹⁶					X	X	X	X	X
SOWS ¹⁷		X						X	X	X	X	
PK blood sample collection			X ¹⁸	X ¹⁹	X	X		X	X			X
Discontinue current analgesics			X									
Dispense/review/collect/instruct study drug			X	X	X	X	X	X ²⁰	X ²¹			X
Opioid side effect training			X									
Abuse & diversion assessment				X	X	X	X		X			X
Concomitant medications ²²			←									X
Adverse events ²²			←									X

Abbreviations: ALP, alkaline phosphatase; ALT, alanine aminotransferase; AST, aspartate aminotransferase; BMI, body mass index, COWS, Clinical Opiate Withdrawal Scale; eC-SSRS, electronic Columbia–Suicide Severity Rating Scale; ECG, electrocardiogram, EOS, end of study; EOT, end of treatment; ET, early termination; mBPI-SF, modified Brief Pain Index-Short Form; MSE, morphine sulfate equivalent; NRS numerical rating scale; PHQ-8, Personal Health Questionnaire Depression Scale PK, pharmacokinetic; SOWS, Subjective Opiate Withdrawal Scale; TBL, total bilirubin.

* If at any time a subject does not tolerate study drug between protocol-mandated visits in the Treatment Period, per Investigator discretion, an unscheduled visit should occur.

FOOTNOTES:

1. There is no Visit 2 for Rollover Subjects.
2. If a subject was dosed with study drug and discontinues from the study before completing all of the scheduled assessments, then assessments for Visit 21/ET and all safety follow-up procedures should be completed for this subject.

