Subjects will return to the clinic for assessments of tolerability and effectiveness every 4 to 10 days for up to 6 more times over a 5-week period until a stable dose is achieved. A **stable** dose is a dose that is effective and tolerated on two sequential visits (i.e., after at least 8 days of continuous treatment). Subjects who continue to tolerate study drug but do not have adequate relief of pain, based on the Investigator's clinical judgment, will continue dose escalations of 100-mg BID increments until the maximum dose of 600-mg NKTR-181 BID is reached.

Subjects who do not achieve adequate pain control at 600-mg NKTR-181 BID will be classified as non-responders and will be discontinued from further participation in the study.

Non-responders will be required to complete the ET Visit (Visit 21/ET) and safety follow-up requirements.

Subjects will begin a monthly clinic visit schedule after a tolerable, effective and stable dose is achieved. **Doses of NKTR-181 may be adjusted upwards (up to a maximum dose of 600-mg NKTR-181 BID) or downwards as needed during the Treatment Period, based on the Investigator's (or qualified sub-Investigator's) assessment of effectiveness and tolerability.**

If at any time a subject cannot tolerate study drug between protocol-mandated visits, per Investigator discretion, an unscheduled visit should occur. For subjects with tolerability issues, the dose of NKTR-181 may be adjusted downwards, as necessary, based on the Investigator's clinical judgment in a stepwise 100-mg changes (e.g., 300-mg BID may be lowered to 200-mg BID). Dose adjustments may occur at unscheduled visits, however, an unscheduled visit will not replace a regularly scheduled visit, and the subject should be seen at all regularly scheduled visits.

Throughout the Treatment Period, subjects who experience breakthrough pain will be allowed rescue medication, as outlined in Section 6.4. Note: If subject is off of study drug for 3 days or more, sponsor **must** be consulted prior to restarting study drug.

Subjects will report their pain experience at each visit using the mBPI-SF. At quarterly intervals, subjects will be assessed for vital signs, 12-lead electrocardiogram (ECG), and clinical laboratory testing.

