9.0 EFFICACY ASSESSMENTS

9.1 Modified Brief Pain Inventory-Short Form (mBPI-SF)

The mBPI-SF ([Mendoza, 2006](#)) was developed to provide information on pain intensity and the degree to which pain interferes with patient functioning. Using a 0 to 10 numerical rating scale (NRS), subjects rate their pain at the time of responding to the questionnaire (Pain Now), and also at its worst, least, and average over the previous 24 hours. With 0 being "no interference" and 10 being "interferes completely," the mBPI-SF asks for ratings of the degree to which pain interferes with mood, walking and other physical activity, work, social activity, relations with others, and sleep.

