11.10 Efficacy Analyses

11.10.1 Modified Brief Pain Inventory–Short Form

The mBPI-SF will be assessed at each visit during the study. The change from baseline and value at each visit will be summarized descriptively over time.

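### The Schedule omits the mBPI-SF at Visit 21/ET although the protocol text and the SAP expect it, and the SAP neither defines the end-of-study time point nor marks Visit 22 as post-taper

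*SAP*

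**What the plan says.** **Taper.** Protocol 6.2 states: "Following 51 weeks of NKTR-181 treatment, subjects will begin a 1-week taper from study drug". It continues: "The NKTR-181 dose will be decreased over the 1-week period until all subjects are receiving 100-mg BID for at least 2 days". Visit 22/EOT follows. The Schedule (Protocol 1.2) puts Visit 21 at D357 and Visit 22 at D364.

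**When pain is scored.** The mBPI-SF row of the Schedule is marked at Visit 3, Visits 4 to 9, Visits 10 to 20, Visit 22/EOT and unscheduled visits. The 21/ET cell is empty. Protocol 6.2 says otherwise: "Subjects will report their pain experience at each visit using the mBPI-SF". Protocol 11.10.1 and SAP 8.6 also say every visit, and SAP Table 1 gives Visit 21 an mBPI entry rather than NA.

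**Early exit.** Footnote 2 of the Schedule says that for a dosed subject who leaves early, "assessments for Visit 21/ET and all safety follow-up procedures should be completed for this subject". That is the column without an mBPI-SF.

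**Recall period.** Subjects rate current pain and pain at its "worst, least, and average over the previous 24 hours" (Protocol 9.1).

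**Analysis.** SAP 8.6 summarises the mBPI-SF by visit and adds an exploratory MMRM with LS means over time, introduced by "The change from baseline to the end of the long term safety study will be analyzed". SAP 8.6.1 computes responder rates at each time point with the whole analysis set as denominator, and counts a missing score or a prior discontinuation as non-response.

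**The concern.** Visit 21 is the last visit before the taper and also the visit at which discontinuers are seen. If sites follow the Schedule, no pain score is collected there. The final weeks at the titrated dose then have no score, and subjects who leave early have no exit score.

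The one later scheduled score, at Visit 22, describes pain at the common taper dose, yet neither document marks it as different from the visits before it. A reader who sees a row for Visit 22 at week 52 of a 52-week study could take it as effectiveness at the titrated dose. Some SAP 8.6 and 8.6.1 results are also presented by dose level, which makes that misreading easier: a subject labelled by the titrated dose is not on it at Visit 22, unless that dose was 100 mg BID.

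The mBPI-SF is the only efficacy endpoint and serves the secondary objective.

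**Working it through.** **1. The visit days reproduce.** 51 weeks × 7 = 357 days (Visit 21) and 52 × 7 = 364 days (Visit 22). The taper occupies the week between them.

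**2. What a Visit 22 score measures.** All completers have been on 100 mg BID for at least 2 days and the recall period is 24 hours. Because 2 days exceeds 24 hours, the whole recall window lies at 100 mg BID. As a share of the titrated dose this is 100/600 = 17%, 100/400 = 25%, 100/200 = 50%, or 100/100 = 100%. A subject maintained on 100 mg BID has no dose change.

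**3. Is the blank cell a misreading of the table?** The mBPI-SF row has 12 cells for 12 columns, and the 21/ET cell is empty. Setting the Visit 21 entries side by side:

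| Assessment | Schedule, 21/ET | SAP Table 1, Visit 21 |
|---|---|---|
| Laboratory tests | marked | actual visit |
| Vital signs | blank | NA |
| ECG | blank | NA |
| C-SSRS | marked | actual visit |
| COWS | marked | actual visit |
| mBPI-SF | **blank** | **actual visit** |

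Five of six agree. Only the mBPI-SF conflicts.

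**4. How much is captured before the taper.** Scheduled post-baseline scores are Visits 4 to 9 (6), Visits 10 to 20 (11) and Visit 22 (1), a total of 18 if every visit occurs. 6 + 11 = 17 precede the taper and 1 follows it.

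**5. The gap before D357.** SAP Table 1 sets Visit 10 as Day 1 and Visit 20 as Day 300, so Visit 20 = Visit 10 + 299 days. The documents do not fix the titration day of Visit 10. From Protocol 6.2, I assume Day 9 (a stable dose after at least 8 days) to Day 46 (10 days to the first return, plus 5 weeks, after Day 1).

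- Visit 10 on Day 9: Visit 20 on Day 308, and 357 − 308 = 49 days.
- Visit 10 on Day 46: Visit 20 on Day 345, and 357 − 345 = 12 days.
- With all ten monthly visits 3 days early (10 × 27 = 270 days after Visit 10): Visit 20 on Day 279 to 316, a gap of 78 to 41 days.

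Visit 20 precedes D357 only if Visit 10 is on or before Day 57, since 57 + 299 = 356.

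**6. Responder rate at Visit 21.** The SAP 8.6.1 rate is responders divided by all subjects in the analysis set, times 100, with a missing score counted as non-response. With no scores collected it is 0/N × 100 = 0% for any N. If only some sites collect the form, the rate cannot exceed the share of subjects with a score, so it partly reflects site practice.

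**7. Rollover baseline.** Under Protocol 6.1.1, Visit 3 is the feeder study's End of Treatment Visit, after tapering to 100 mg BID. For Rollover Subjects from the NKTR-181 arm, a change from Visit 3 to Visit 22 therefore compares two post-taper scores.

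**8. Where an exit score would go.** For Visit 21, SAP Table 1 follows the actual visit. A score recorded under 21/ET in any earlier week could therefore be pooled with completers' D357 scores.

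**The case against.** The strongest reply is that the endpoint is the mBPI-SF by visit, and by-visit results through Visit 20 describe maintenance-dose pain. That stands. A reader might infer that the efficacy endpoint fails to capture maintenance-dose pain at all. The count of 17 in 18 rules that out, and only the last weeks before the taper are at issue.

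A reader might also take the end of the study to mean Visit 22. The SAP never says so. What can be shown is that the time point is undefined and that, under the Schedule, Visit 22 is the only scheduled score after Visit 20.

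Nor is the missing Visit 21 score a settled omission. The narrative text of both documents and SAP Table 1 point the other way, so the defect is an unreconciled conflict.

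Early exits are not ignored. SAP 8.6.1 counts them as non-responders, and SAP 8.6.3 analyses time to discontinuation, including for lack of efficacy. Unscheduled visits also carry the mBPI-SF. A missing exit score therefore affects only the exploratory MMRM and the by-visit means.

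The comparison of 100 mg BID with 100 mg BID cannot be extended to all Rollover Subjects. Protocol 6.1 admits subjects from the placebo arm as well, and what they took during the feeder taper is not stated here.

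Finally, this is an uncontrolled safety study with no formal sample size calculation. That limits the weight of the point, but it does not resolve the conflict.

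**Conclusion.** The point holds in a limited form and should be corrected. The Schedule conflicts with Protocol 6.2, Protocol 11.10.1, SAP 8.6 and SAP Table 1 on whether the mBPI-SF is completed at Visit 21/ET. If the Schedule is followed:

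- maintenance-dose pain is recorded through Visit 20 but not at D357 or at early exit;
- the only later scheduled score is post-taper and unlabelled;
- a Visit 21 responder rate, if computed, is 0% by construction.

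Independently of that conflict, SAP 8.6 leaves the end-of-study visit undefined, and the Visit 3 to Visit 22 change in NKTR-181-arm Rollover Subjects compares two post-taper scores.

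The 12 to 49 day gap rests on the assumed day of Visit 10 and on SAP Table 1 spacing. The 0% rests on no score being collected and on Visit 21 being treated as a time point.

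The documents do not support a figure for how far the Visit 22 mean or responder rate would differ from the maintenance-dose value. They give no mBPI-SF variability and no data on pain after dose reduction, and the Phase 2 reduction in Protocol 2.3 is for daily pain during titration in knee osteoarthritis. Nor do they support a count of exits without a score, because the exposure targets in Protocol 11.2 are minimums and not dropout forecasts.

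**What to change.** (a) **Schedule.** Reconcile the sections by marking the mBPI-SF at Visit 21/ET, completed before any taper drug is taken.

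(b) **SAP 8.6 and 8.6.1.** Define the end-of-treatment efficacy time point as Visit 21, before the taper. If Visit 21 scores were not collected, use Visit 20 for all subjects, so that scores from different weeks are not mixed, and do not compute a Visit 21 responder rate. Report Visit 22 separately under a post-taper label, outside the end-of-treatment LS mean and responder rate.

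(c) **SAP Table 1.** Assign an early-termination mBPI score to the visit window containing its study day, and do not pool it with the D357 Visit 21 row. SAP 7.2 counts study days from Visit 10, so also state where a score from an exit before Visit 10 belongs.

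The cost is one short self-completed questionnaire at an existing visit, a minor Schedule amendment and some SAP wording. If scores can no longer be added, (b) with the Visit 20 fallback needs only SAP text. Sample size and dosing do not change.
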